12.3 Analysis of Primary Endpoints

Pilot Phase

To address the safety of both regimens, a maximum width 90% confidence interval for any grade 3 or higher toxicity will be approximately 30%. For 35 patients in this study, if the true unknown probability of a rare toxicity is 10%, the probability of observing 1 or more toxicities is 97%, and if the true toxicity rate is 5% then the probability of observing one or more rare toxicities is 83%.

In the first cohort, because the study participants are awaiting a curative surgery, greater than 10% delay in surgery (more than 2 weeks) is unacceptable. Thus, if ≥ 2 delays are observed in the first ten participants, the dose will be de-escalated to level -1. If ≥ 2 additional delays are observed after dose modification, consideration will be made to further change in dose or schedule of study medication.

Phase II

Regarding the ER and Ki67 analysis, we will also include the evaluable patients from the pilot phase for this analysis. For the evaluation of these biological endpoints, the analysis will include ALL of the patients in both cohorts (the first cohort-operable stage I-II and the second cohort-unresectable locally advance/metastatic) as well as both anastrozole and tamoxifen groups. When the sample size is 41, a single-group repeated measures analysis of variance with a 0.05 significance level will have adequate above 80% power to detect a difference in average expression levels of ER and Ki67 between the baseline and after treatment values when an effect size is 0.1. With effect size of 0.125 and higher, power increases to 90%.

The 95% confidence intervals will be constructed for the observed proportions. Exploratory data analysis and appropriate graphs will be used to decide whether data transformation (e.g. log or square-root) is necessary to assure an approximate normality. All descriptive statistics will be reported for ER and Ki67 expression. We will use general linear model approach and/or its non parametric alternative, the Wilcoxon test, to assess whether there is any evidence of changes due to treatment. All statistical tests will be two-sided done at the 0.05 level of significance. Statistical analysis will be done using S-plus (TIBCO version 8.0).

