1	5 mg weekly (on day 1, 8, 15, 22, and 29)	1

or

Dose Modification Schema for Premenopausal Women		
Dose Level	Dose	
	Entinostat (mg)	Tamoxifen (mg) daily
-1	3 mg weekly (on day 1, 8, 15, 22, and 29)	20
1	5 mg weekly (on day 1, 8, 15, 22, and 29)	20

In the phase II part, the Simon's two-stage design will be used for the study to ensure that the number of patients exposed to this new treatment is minimized. The analysis for this part of the study will include ALL of the patients in both cohorts (the first cohort-operable stage I-II and the second cohort-unresectable locally advance/metastatic) as well as both anastrozole and tamoxifen groups. The total sample size for the phase II part of the study is 32 with 12 and 20 patients in the first and second stage respectively. The 6 patients in the pilot phase of each combination that are treated with the recommended dose level for phase II will be included in the first stage of the phase II part of the study. The study will be terminated, if there is no response among the first 12 patients. If ≥ 1 response in these 12 patients is observed, then 20 more patients will be accrued. The combination will be considered promising, if ≥ 4 out of 32 patients have a response. This design yields 87% power. The probability of early stopping and declaring that this combination has no sufficient activity is 0.54, if the true success rate is 5% and 0.07 if the true response rate is 20%. If the true proportion of patients with Ki67 reduction combined with ER up-regulation is 0.20, the probability of concluding that the drug has sufficient activity is 0.87 and 0.07 if the true proportion is 0.05. To allow about 10% inevaluability, the phase II trial will accrue 35 eligible patients. Statistical analysis will be done using S-plus (TIBCO, version 8.0). All descriptive statistics will be reported. The multivariate analysis of variance or its non-parametric alternative will be applied to compare biomarkers' expression levels. The 90% confidence intervals will be constructed for the observed proportions. All statistical tests will be two-sided, and done at the 0.05 level of significance.

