12.2 Sample Size/Accrual Rate

For the pilot phase, the study will require 12-24 patients to complete, allowing for 3-6 patients per dose level and 2 predefined dose levels for 2 combination treatments (entinostat and anastrozole as well as entinostat and tamoxifen). In the phase II period, the study will require 12-35 patients to complete. However, we will include the 12 patients in the pilot phase that are treated with the recommended dose level of each combination for phase II in the primary endpoint analysis. Therefore, the total sample size for this study is 12-41 patients. At an anticipated accrual rate of 15-20 patients/year, we anticipate that the phase II part will need to accrue patients for anywhere from 7 to 33 months.

NOTE: The maximum total sample size will most likely remain 41 patients. The only situation that this trial will require additional 6 patients is that there are ≥ 2 patients in the first cohort of 6 patients suffer DLT in dose level 1 in both combination treatments. As of November 2011, there were 3 patients enrolled in the pilot phase of this study. There is no DLT observed in this first 3 patients treated with entinostat and anastrozole. Furthermore, a phase II study of

entinostat and AIs including anastrozole was recently completed which demonstrated that this combination is safe and tolerable with the majority of AEs being only grade 1 or 2⁴⁷. Taken this together, it is highly unlikely that there will be ≥ 2 patients in the first cohort of 6 patients suffer DLT in dose level 1 in entinostat and anastrozole group.

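### Ki67/ER mean-change power is quoted at 41, an enrolment total; at the roughly 32 evaluable pairs the plan itself expects, power at effect size 0.1 falls below 80%

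*Combined protocol and SAP*

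**What the plan says.** Section 1.1 makes change in Ki67, and ER expression after treatment, the phase II primary objectives. Section 12.3 gives the only power statement for mean change in these markers: "When the sample size is 41, a single-group repeated measures analysis of variance with a 0.05 significance level will have adequate above 80% power", for a baseline-to-post-treatment difference at effect size 0.1. It adds: "With effect size of 0.125 and higher, power increases to 90" per cent. It gives no definition of the effect size, no SD and no within-patient correlation.

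The number 41 comes from Section 12.2: "Therefore, the total sample size for this study is 12-41 patients". A note there says "The maximum total sample size will most likely remain 41 patients" and that a further 6 would be needed only if both combinations de-escalate ("The only situation that this trial will require additional 6 patients is that there are" at least two DLTs among the first six in each). For the anastrozole group the note dismisses that event: "Taken this together, it is highly unlikely that there will be" that many.

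Section 12.1 sets the phase II target at 32 and inflates it: "To allow about 10% inevaluability, the phase II trial will accrue 35 eligible patients".

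On which pilot patients count, Sections 12.1 and 12.2 name those at the recommended dose ("we will include the 12 patients in the pilot phase that are treated with the recommended dose level of each combination"). Section 12.3 admits evaluable pilot patients to the ER and Ki67 analysis without a dose restriction.

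**The concern.** A before/after analysis uses pairs, not enrolled patients. Section 12.1 accepts that about one patient in ten will not be evaluable, and Section 5.1 lets a second-cohort patient stay on treatment when no post-treatment biopsy can be done. The Section 12.3 power figure makes no such deduction. It also takes the enrolment total that arises only if one combination de-escalates.

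The risk is one of interpretation. A non-significant mean change in Ki67 or ER on about 32 pairs would be read against 80-90% power that a sample of that size does not provide.

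**Working it through.** **Where 41 comes from.** Section 12.2 gives 12-24 pilot patients, up to 35 in phase II, and 12 pilot patients counted in both. The totals below are derived from these; the plan does not set them out.

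- No de-escalation: 12 + 35 - 12 = 35 enrolled
- One combination de-escalates: 18 + 35 - 12 = 41
- Both de-escalate: 24 + 35 - 12 = 47

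The note in Section 12.2 fits this: the further 6 beyond 41 arise only when both de-escalate.

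**Expected pairs.**

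- 35 enrolled: 32, from Section 12.1.
- 41 enrolled, only recommended-dose pilot patients analysed: 41 - 6 = 35, so again 32.
- 41 enrolled, all evaluable pilot patients analysed: 41 × 0.9 = 36.9, or 41 - 3 = 38 if only the phase II allowance (35 - 32 = 3) is lost.
- 47 enrolled, all doses analysed: 47 × 0.9 = 42.3, or 47 - 3 = 44.

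**Method.** One group at two time points is a paired t test. With δ = mean change / SD of change, power is the probability that a noncentral t (n - 1 df, noncentrality δ√n) exceeds the two-sided 0.05 critical value in absolute size.

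**Reproducing the plan at n = 41.** The metric is not given, so these readings are assumptions.

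- Variance ratio: effect size = variance of the two means / [σ²(1 - ρ)], so δ² = 2 × effect size. At 0.1, δ = √0.2 = 0.447 and power is 79.8%; at 0.125, δ = 0.500 and power is 87.8%. This is close to the stated figures but slightly under both.
- Eta-squared type: δ² = 2 × effect size / (1 - effect size). At 0.1, δ = √(0.2/0.9) = 0.471 and power is 83.8%; at 0.125, δ = √(0.25/0.875) = 0.535 and power is 91.6%. This meets both stated figures.
- Variance-ratio scaling fitted to the stated 90% at 0.125: δ = 0.519 × √(0.1/0.125) = 0.464, power 82.6% at 0.1. Because it is fitted to the plan's figure, it does not independently reproduce it.

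Other common readings do not fit. δ = 0.1 gives 9.6%. Cohen's f = 0.1 gives 24.0% with ρ = 0.5. With ρ = 0.9 it gives 79.8%, but then 93.7% at 0.125.

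**Power at the expected pairs.** The last two rows need no metric: they take a change with exactly 80% or 90% power at 41 pairs and carry it to smaller n.

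| Case | δ | 41 pairs | 38 | 37 | 32 |
|---|---|---|---|---|---|
| 0.1, variance ratio | 0.447 | 79.8% | 76.6% | 75.4% | 68.8% |
| 0.1, fitted to 90% at 0.125 | 0.464 | 82.6% | 79.6% | 78.4% | 72.0% |
| 0.1, eta-squared type | 0.471 | 83.8% | 80.8% | 79.7% | 73.3% |
| 80% at 41 | 0.448 | 80.0% | 76.8% | 75.6% | 69.1% |
| 90% at 41 | 0.519 | 90.0% | 87.6% | 86.7% | 81.1% |

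**Power needed at 41 to keep 80%.** For 80% at 32 pairs it is 89.1%, which is practically the figure the plan gives for 0.125 rather than 0.1. For 37 or 38 pairs it is 84.1% or 83.1%, which a claim of more than 80% does not rule out.

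**Detectable δ for 80% / 90% power.** 0.51 / 0.59 at 32 pairs; 0.47 / 0.55 at 37; 0.45 / 0.52 at 41.

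**The case against.** The power statement is conditional on a sample of 41, and under plausible readings it is about right for 41 pairs. A reader might infer that Section 12.3 contains a miscalculation. The documents do not support that: one reading meets both stated figures and another comes within about 2 points of each. The weakness lies in the n chosen. This part of the objection stands.

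It is also fair that 32 is the Simon target and not necessarily the number for this analysis. The paragraph with the power statement is the one that admits evaluable pilot patients without a dose limit, and 41 = 35 + 6 suggests that its writer meant to count them. On that reading, with one de-escalation, 37-38 pairs are expected and power may still reach 80%. A reader might infer that power is short in every scenario; that goes too far. If both combinations de-escalated and all doses were analysed, 42-44 pairs would give about 81-86% across the readings above, although Section 12.2 treats de-escalation with anastrozole as remote.

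The missing-biopsy provision concerns the second cohort only. Section 9.1 requires post-treatment tissue from everyone, and in the first cohort it comes from the surgical specimen. No loss beyond the plan's own 10% is shown, and none is assumed here.

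The objection does not rescue 41 as a number of pairs. That still needs one de-escalation, patients at the abandoned dose included, and no inevaluable patient, which is contrary to the allowance in Section 12.1.

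**Conclusion.** The concern holds as a conditional statement. At about 32 pairs, which is what the plan expects with no de-escalation or with recommended-dose pilot patients only, power at effect size 0.1 is below 80%: about 69-73% under readings that give about 80-84% at 41. The power stated as 90% becomes about 81%. At 37-38 pairs power at 0.1 is about 75-81%, so a shortfall is possible but depends on a metric the plan does not define.

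This rests on a paired t test at two-sided 0.05, the plan's own inevaluability allowance, and the enrolment totals derived above. A reader might also infer that the go/no-go decision is underpowered. It is not touched: the Simon rule uses a binary response and is already built on 32 patients.

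**What to change.** In Section 12.3:

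- Define the effect size actually used, either with its SD and correlation or as mean change divided by the SD of change, on the scale to be analysed.
- Restate power, or the detectable paired change, at the expected evaluable pairs: 0.51 (80%) and 0.59 (90%) at 32, and 0.47 and 0.55 at 37 if all evaluable pilot patients count. The corresponding values at 41 are 0.45 and 0.52.
- Reconcile Sections 12.1 and 12.2 with Section 12.3 on whether pilot patients treated at a dose not carried forward enter the Ki67/ER mean-change analysis.

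The change is to wording only. It needs no extra patients and leaves the Simon rule and its population as they are. The cost is a less favourable stated power.

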12.4 Analysis of Secondary Endpoints

Baseline and after treatment PR, HER2, EGFR, CK5/6, aromastase, tissue histone H3 and H4 acetylation will be treated as continuous variables. We may also use the multivariate analysis of variance to compare correlated biomarkers' expression. Correlation between biomarkers will be estimated and tested. The repeated measures model approach will be also used. Categorical outcome data (e.g., number of proteins expressed) will be recorded, proportions will be estimated and compared using the Fisher's exact test.

Clinical and pathological response rate with the corresponding 90% or 95% CI will be estimated for all eligible patients. The possible association between response rate and dose level will also be assessed.

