First Cohort: Operable stage I-II triple negative breast cancer (ER, PR, and HER2 negative) in pre- and postmenopausal women

Second Cohort: Unresectable locally advanced or stage IV metastatic triple negative breast cancer in pre- and postmenopausal women with ≤ 2 previous systemic chemotherapy and accessible tumors for biopsies, excluding bone only metastasis

Sample size: 12-41 patients

Schema:

* As per recommended dose for phase II

* **For premenopausal patients, tamoxifen 20 mg oral daily will be used instead of anastrozole.

*** ≥ 3 unstained slides of 5 micron thickness

REGIMEN DESCRIPTION					
Agents	Premedications/Precautions	Dose	Route	Schedule	Length of Treatment
Entinostat	Taken with a meal after the first two or three bites	*** mg	oral	weekly starting on day 1	15-29 days (Preferably 22 days)
Anastrozole	-	1 mg once daily	oral	everyday starting on day 4	
Tamoxifen	-	20 mg once daily	oral	everyday starting on day 4	
***Doses as appropriate for assigned dose level.					

Dose Modification Schema for Postmenopausal Women		
Dose Level	Dose	
	Entinostat (mg)	Anastrozole (mg) daily
-1	3 mg weekly (on day 1, 8, 15, 22, and 29)	1
1	5 mg weekly (on day 1, 8, 15, 22, and 29)	1

Dose Modification Schema for Premenopausal Women		
Dose Level	Dose	
	Entinostat (mg)	Tamoxifen (mg) daily
-1	3 mg weekly (on day 1, 8, 15, 22, and 29)	20
1	5 mg weekly (on day 1, 8, 15, 22, and 29)	20

TABLE OF CONTENTS

SCHEMA	4
1. OBJECTIVES	8
1.1. Primary Objectives	8
1.2. Secondary Objectives	8
1.3. Exploratory Objectives	8
2. BACKGROUND	8
2.1 Epigenetics	8
2.2 Histone Modification and Epigenetics	9
2.3 Triple Negative Breast Cancer	9
2.4 Entinostat Clinical Experience	9
2.5 Rationale	10
2.6 Correlative Studies Background	13
3. PATIENT SELECTION	14
3.1 Inclusion Criteria	14
3.2 Exclusion Criteria	16
3.3 Inclusion of Minorities	16
4. REGISTRATION PROCEDURES	16
4.1 General Guidelines	16
4.2 Pretrial Screening	17
5. TREATMENT PLAN	17
5.1 Agent Administration	17
5.2 Study Plan	19
5.3 General Concomitant Medication	21
5.4 Duration of Therapy	21
5.5 Surgical Considerations for the First Cohort (Operable Stage I-II)	21
5.6 Postoperative Treatments	22
5.7 Duration of Follow Up	22
5.8 Criteria for Removal from Study	22
6. DOSING DELAYS/DOSE MODIFICATIONS	22
6.1 Recommended Dose Adjustments	22
6.2 Supportive Care Guidelines	24
7. ADVERSE EVENT REPORTING AND DATA SAFETY AND MONITORING PLAN	24
7.1 Adverse Events (AEs)	24
7.2 Expedited reporting of severe adverse events	25

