1.2. Secondary Objectives

1. To evaluate baseline and change in the expression levels of progesterone receptor (PR), human epidermal growth factor receptor 2 (HER2), epidermal growth factor receptor (EGFR), cytokeratin 5/6 (CK5/6), and aromatase before and after treatment with entinostat and anastrozole/tamoxifen.
2. To assess baseline and change in tumor tissue histone H3 and H4 acetylation before and after treatment with entinostat and anastrozole/tamoxifen.
3. To assess the clinical and pathological response to preoperative combination of entinostat and anastrozole/tamoxifen in TNBC.

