- Treatment will be started after pretreatment biopsy and will be continued until disease progression. The post-treatment biopsy (biopsy#2) will be performed after a minimum of 15 days and a maximum of 29 days of treatment, but preferably close to 29 days. The post-treatment biopsy must take place within 6 days (preferably within 3 days) after the last dose of entinostat. After the post-treatment biopsy, treatment will be continued until disease progression regardless of the result of post-treatment biopsy. Restaging scans will be performed every 6 weeks while on treatment. In the event that a patient cannot undergo the post-treatment biopsy for any reason, they will continue to be treated per study protocol. If a patient discontinues the study prior to 15 days, an attempt should be made to collect the biopsy when the decision is made to discontinue and prior to initiation of additional treatment, if possible.
 - Anastrozole will be administered continuously starting on day 4 at a fixed dose of 1 mg oral once daily until disease progression.
 - In patients who are not postmenopause as defined by any of the previously described criteria, tamoxifen will be administered continuously instead of anastrozole starting on day 4 at a fixed dose of 20 mg oral once daily until disease progression.
 - Entinostat will be administered at the assigned dose once a week until disease progression. Entinostat should be taken with a meal after the first two or three bites.
 - The initial starting dose for entinostat is 5 mg oral weekly. Dose de-escalation to 3 mg/week is permitted if dose limiting toxicity is observed as defined in section 5.2.1.
 - Dose level for entinostat in phase II part of this study will be determined after the pilot phase is completed.

The dose schemas are as shown below for both postmenopausal and premenopausal women:

Dose Modification Schema for Postmenopausal Women		
Dose Level	Dose	
	Entinostat (mg)	Anastrozole (mg) daily
-1	3 mg weekly (on day 1, 8, 15, 22, and 29)	1
1	5 mg weekly (on day 1, 8, 15, 22, and 29)	1

or

Dose Modification Schema for Premenopausal Women		
Dose Level	Dose	
	Entinostat (mg)	Tamoxifen (mg) daily
-1	3 mg weekly (on day 1, 8, 15, 22, and 29)	20
1	5 mg weekly (on day 1, 8, 15, 22, and 29)	20

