9.1.1 Collections

In the first cohort:

Tumor tissue samples from the following time points will be obtained:

1. Prior to starting treatment or tissue sample at the original diagnostic procedure. (T0)
2. At the time of definitive surgery (i.e., mastectomy or lumpectomy). A separate tumor biopsy is not needed on the day of surgery; tissue will be taken from the surgical specimen. (T1)

Note: If a subject receives additional preoperative treatment after discontinuing study treatment and prior to surgery, every attempt should be made to collect a tissue sample for the study prior to initiation of the new treatment; in these cases, tissue will still be collected at the time of definitive surgery, as above.

Every effort should be made to provide a core specimen from the surgical sample after treatment. The site pathologist should remove a core samples during the dissection of the surgical specimen (using a 5-mm skin punch biopsy device). The samples should be processed preferably within 1 hour, but may be processed up to 2 hours of removal from the patients. This core specimen should be fixed in formalin and processed separately as per the American Society of Clinical Oncology/College of American Pathologists Guideline Recommendations published in Journal of Clinical Oncology 2010⁴².

In the second cohort:

Approximately six core biopsy specimens will be obtained with each biopsy. Alternative to core needle biopsy, fine needle aspirate (FNA) is allowed in this cohort of patients. Cytology cell blocks should be made from FNA specimens using routine institutional cytology protocol. Biopsy should be obtained from soft tissue metastasis such as breast, liver, skin, lung, or intra-abdominal implants. Bone biopsy, paracentesis (ascites), and thoracocentesis (pleural effusion) specimens are not adequate.

Tumor tissue samples from the following time points will be obtained:

1. Pretreatment biopsy (biopsy#1) will be performed within 3 weeks after registration. However, the pretreatment biopsy can be omitted in patients who have recent biopsy but have not been started on breast cancer treatment within 12 weeks prior to the registration and there is adequate tumor tissue sample as per section 3.1.9. (T0-Second cohort)

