11.1 Pathologic Response Determination

Pathological response in the breast, and when appropriate, in the axilla will be assessed.

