11.2 Clinical Response Determination

Clinical response in the breast will be evaluated, and when appropriate, in the axilla, infraclavicular, supraclavicular regions, and skin. At the time of study enrollment, patients will have a breast examination. Physical examination findings will be documented including clinical tumor size, character, mobility, and location of the breast mass. In addition, T4 features must be described. The patient will be examined by one of the treating investigators or his/her designee at each specified time point and at the time of the surgery.

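### Section 12.4 puts second-cohort patients, who have no planned surgery, in the denominator of the pathological response rate; for clinical response the denominator rule is missing

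*Combined protocol and SAP*

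**What the plan says.** Section 12.4 sets one analysis set for both response endpoints: "Clinical and pathological response rate with the corresponding 90% or 95% CI will be estimated for all eligible patients". It does not restrict by cohort, by whether surgery took place or by whether the patient could be assessed.

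The objective behind these endpoints is the third item of section 1.2: "To assess the clinical and pathological response to preoperative combination of entinostat and anastrozole/tamoxifen in TNBC".

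The Schema describes the second group of patients as follows: "Second Cohort: Unresectable locally advanced or stage IV metastatic triple negative breast cancer in pre- and postmenopausal women". Section 5.1 plans no surgery for them: "After the post-treatment biopsy, treatment will be continued until disease progression regardless of the result of post-treatment biopsy". Their post-treatment tissue is a needle sample, and section 9.1.1 goes below a core: "Alternative to core needle biopsy, fine needle aspirate (FNA) is allowed in this cohort of patients".

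Section 11.1 places the pathological endpoint anatomically: "Pathological response in the breast, and when appropriate, in the axilla will be assessed". Section 12.1, in defining the composite response, ties pathological complete response to surgical specimens taken after treatment.

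Section 11.2 opens with "Clinical response in the breast will be evaluated" and, in the same sentence, adds the axilla, the infraclavicular and supraclavicular regions and the skin where appropriate. The categories in section 11.2.1 rest on palpation and ruler measurement and are worded for the breast. They include an inevaluable category (cID) for cancer that cannot be palpated in two dimensions.

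**The concern.** A response rate is interpretable when everyone in the denominator could have had the event. For pathological response that is true of the first cohort only. Followed literally, section 12.4 adds patients for whom the endpoint has no specimen. The reported rate then depends on the mix of cohorts enrolled as well as on the treatment, and the interval is computed as if the added patients carried information.

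Section 12.4 also plans to relate response rate to dose level. If the cohort mix differs between dose levels, that comparison inherits the problem.

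**Working it through.** **Plan figures.** Section 12.4 gives no sample size, power or expected rate for these endpoints, so there is nothing to reproduce for them directly. The two-stage design in section 12.1, which drives enrolment, can be checked by exact binomial calculation: n1 = 12, stop if there are 0 responses, n = 32, promising if there are 4 or more.

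- Early stopping, (1−p)^12: 0.95^12 = 0.540 and 0.80^12 = 0.069 (plan 0.54 and 0.07).
- Declared promising, the sum over x = 1 to 12 of P(X1 = x) × P(X2 ≥ 4−x) with X2 ~ Bin(20, p): 0.065 at p = 0.05 and 0.866 at p = 0.20 (plan 0.07 and 0.87).

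The design reproduces. It concerns the composite response, which a second-cohort patient can meet through Ki67 and ER on a biopsy, so it is not in question here.

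**Inputs for the pathological rate.**

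- N = 35 eligible patients, from section 12.1 (phase II accrual).
- k = number of those in the second cohort. The documents do not give it; a range is assumed.
- p1 = true first-cohort rate. The documents do not give it; 20% is assumed for illustration.
- Second-cohort patients are counted as non-responders.

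**Formula.** Pooled rate = p1 × (N − k)/N. The factor is the first cohort's share, so it depends on N only through that share.

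| k | Factor (35 − k)/35 | A true 20% is reported as |
|---|---|---|
| 10 | 25/35 = 0.71 | 14.3% |
| 17 | 18/35 = 0.51 | 10.3% |
| 25 | 10/35 = 0.29 | 5.7% |

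**Effect on the interval.** Take 17 first-cohort patients, 18 second-cohort patients and 3 responders (hypothetical). Intervals are Clopper-Pearson; both levels are shown because section 12.4 leaves the choice open.

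| Denominator | Rate | 95% CI | 90% CI |
|---|---|---|---|
| First cohort, 3/17 | 17.6% | 3.8% to 43.4% | 5.0% to 39.6% |
| All eligible, 3/35 | 8.6% | 1.8% to 23.1% | 2.4% to 20.7% |

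The 95% width falls from 39.6 to 21.3 percentage points only because 18 patients with no observable endpoint were added.

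**Clinical response, by reading.** Several provisions make part of the second cohort assessable:

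- Section 3.1.12 admits local-regional recurrence.
- The second-cohort calendar in section 10 has palpable or visible tumours measured.
- Section 11.2 extends to regional nodes and skin.

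The patients left out are those without palpable breast, regional or skin disease. For them section 11.2.1 offers cID but no rule on the denominator. Counted as non-responders, they lower the rate, by at most the factors above. Excluded, they leave it unchanged. Read literally, the clinical complete response definition (nothing abnormal to palpate) could even be met by a metastatic patient with no breast lesion, which would raise the rate. Restaging scans are done every 6 weeks, but section 11 has no criterion that uses them.

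**The case against.** The strongest reply is that context already limits these rates to the surgical cohort. Where the plan pools cohorts, in sections 12.1 and 12.3, it does so in explicit words and for the biological endpoints and the two-stage analysis. The response sentence in section 12.4 does not repeat those words. The objective speaks of preoperative treatment, and section 11 opens with re-evaluation up to surgery. This shows what was probably intended. It does not change the denominator that section 12.4 names, and no other section restricts it. The intent-to-treat notes in section 5.8 do not help, because they concern patients removed from study, not patients for whom surgery was never planned.

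A second reply is that dilution presupposes counting unassessable patients as non-responders, which the plan does not say outright. That stands as a condition. Section 11.1.2 also refers to a pathologic specimen without specifying its type, so a tumour-free needle sample could be scored as a complete response and push the rate up. Sections 11.1 and 12.1 tell against that reading, and either way the second-cohort contribution has no defined meaning.

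A third reply is that the endpoint is secondary and descriptive with no decision rule attached. This is correct and limits the consequence.

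A reader might go further and infer that second-cohort patients cannot respond clinically either, so that both rates are diluted alike. The documents do not support this. Local-regional disease is eligible, skin and regional nodes are covered, palpable tumours are measured, and an inevaluable category exists.

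**Conclusion.** The point holds for pathological response. The named denominator includes patients who, by design, have no surgical specimen. If they are counted as non-responders, the rate is multiplied by the first-cohort share: 0.71, 0.51 or 0.29 with 10, 17 or 25 of 35 patients in the second cohort. The interval is narrower than the information warrants. These sizes illustrate an assumed split and are not predictions.

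For clinical response the finding is narrower: a missing rule for cID patients, criteria worded for the breast, and an effect that is smaller and of undefined direction. Nor should a reader conclude that the go/no-go decision is compromised; it rests on the composite response, and its stated operating characteristics reproduce.

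**What to change.** In section 12.4:

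1. Estimate pathological response in first-cohort patients who started treatment. State how those who have no surgery are counted, and how those who receive other treatment before surgery (foreseen in section 5.7) are counted.
2. Report clinical response separately by cohort, and state whether cID patients stay in the denominator.
3. Report second-cohort restaging results separately, under a response criterion named in section 11.

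The cost is a change of wording, a smaller denominator and a wider interval. Sample size, data collection and the two-stage design are unaffected.
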